12.5.3 Patient-Level Variables

The following summaries will be provided for the Full Analysis Set:

- The number of times a GBCA was used per indication, organ/system imaged, age, gender, BMI, reason for use of GBCA and preference for a particular GBCA based on BMI.
- The number of each type of referring physician (seniority or specialty).
- The quality of the referral during the recruitment period of the study.

- The number of repeat MR examinations that are performed during the recruitment period of the study and a summary of the reasons for repeat exams.

12.6 Effectiveness Variables and Analyses

Effectiveness data will be summarised for all GBCAs pooled, for non-Clariscan GBCAs pooled, and for all individual GBCAs administered during the study, including Clariscan. Statistical differences in image quality and diagnostic confidence between groups (Clariscan vs non-Clariscan GBCAs pooled and Clariscan vs each individual GBCA) will be assessed at an alpha of 0.05. However, no formal statistical hypotheses will be tested and no adjustments will be made for multiplicity.

The following summaries will be provided for the Effectiveness Analysis Set:

- The average image quality.
- The average change in diagnostic confidence (diagnostic confidence using CE-MR enhanced image minus diagnostic confidence using the non-enhanced image).
- The proportion of patients for whom contrast-enhanced MRI changed the diagnosis (asked as a yes/no question on the eCRF).
- The proportion of patients for whom contrast-enhanced MRI increased the confidence in diagnosis (asked as a yes/no question on the eCRF).

Stage 2 analyses (Section 10.2) will be conducted at a later date and will be outlined in a separate analysis plan.

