8.2 Method of Numbering Subjects and Assigning Subjects to Treatment Groups

Subject numbers will consist of 7 digits in total; the first 3 digits to identify the centre and the remaining 4 digits to identify the subject. Centre numbers will be in the format 001, 002, etc. Subject numbers for those who withdraw will not be reused.

Subjects will not be assigned to treatment groups because the choice of GBCA will be made by the investigator at the site as part of clinical practice.

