10 PATTERN OF USE, EFFECTIVENESS, SAFETY, AND OTHER VARIABLES

10.1 Pattern of GBCA Use

[figure not shown]
The pattern of use for GBCAs including Clariscan for MR (MR angiography [MRA]/MRI) examination will be assessed based on the following variables:

1. The number of radiological procedures, including ultrasound, MR, computed tomography (CT) scan, fluoroscopy, X-ray, single-photon emission CT (SPECT), and positron emission tomography (PET) examinations, performed by the study centre during the recruitment period of the study. The number of procedures done by the study centre will be collected once in the study and will be used to assess the percentage and proportion of different procedures performed by the radiology department, including the percentage of MR procedures with or without GBCAs (total GBCAs and individual GBCA).
2. Number of MR machines and staff (nurses and technicians) will be recorded to assess the workload per MRI machine and staff.
3. The number of radiological procedures, including ultrasound, MR, CT scan, fluoroscopy, X-ray, SPECT, and PET examinations, reported by the investigator during the recruitment period of the study. The number of procedures done by the centre will be used to assess the percentage and proportion of different procedures performed by the investigator (radiologist), including the percentage of MR procedures with or without GBCAs (total GBCAs and individual GBCA).
4. Use of GBCAs – Total and individual GBCA (generic GBCA recorded as a separate entity) use as per indication, organ/system imaged, age, gender, body mass index (BMI; <18 is “underweight”, 18 to 25 is “normal”, 26 to 30 is “overweight”, 30 to 40 is “obese”, and >40 is “morbidly obese”), reason for use of GBCA and preference for a particular GBCA due to BMI.
5. Referral pattern for CE-MRI - Following information will be assessed:
 - a. Referring physician
 1. seniority (house officer or equivalent, registrar, consultant, super specialist)
 2. specialty (e.g., cardiologist oncologist)
 - b. The quality of referral will be assessed by the radiologist as follows:
 - 1 = not enough information
 - 2 = have all necessary information

3 = good full detailed information with clear question

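### Section 12.6 assesses differences between non-randomised contrast agents at alpha 0.05 and names no control for confounding, although the likely confounders are already recorded

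*Protocol*

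**What the plan says.** Section 12.6 sets two kinds of contrast for two outcomes: "Statistical differences in image quality and diagnostic confidence between groups (Clariscan vs non-Clariscan GBCAs pooled and Clariscan vs each individual GBCA) will be assessed". The differences "will be assessed at an alpha of 0.05". The next sentence adds: "However, no formal statistical hypotheses will be tested and no adjustments will be made for multiplicity". The listed summaries are group averages and proportions, starting with "The average image quality". Multiplicity is the only adjustment discussed, and it is declined.

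Section 8.2 describes how a patient comes to receive an agent: "Subjects will not be assigned to treatment groups because the choice of GBCA will be made by the investigator at the site". Section 10.1, item 4, lists use of each agent by indication, organ or system, age, gender and BMI, together with "reason for use of GBCA and preference for a particular GBCA due to BMI". In the analysis sections this information returns only in section 12.5.3, as counts: "reason for use of GBCA and preference for a particular GBCA based on BMI".

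Image quality is scored by the local radiologist on a 4-point scale whose wording differs between MRI and MRA (10.2). Diagnostic confidence is scored from 0% to 100% before and after contrast, and the change is analysed. Section 10.2 limits individual-agent reporting of these two outcomes to cohorts of more than 100 cases. Section 12.6 sends only Stage 2 to a separate analysis plan, and section 12.12 measures deviations against the analysis described in the protocol itself.

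**The concern.** When clinicians choose the agent, the groups may differ in features that affect how good an image looks and how much contrast adds. BMI, body region, indication and age are obvious candidates. So are the centre, because each centre's own radiologists do the rating, and the type of examination, because the scale wording differs. If the groups differ on these, two identical agents will show different mean scores.

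A large sample does not help. It shrinks the standard error around a biased difference, so a small imbalance becomes statistically significant. The stake is a statement in the study report that Clariscan differs from other agents, in either direction, when the difference reflects who received which agent and where.

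**Working it through.** **Inputs from the protocol.** Alpha is 0.05; sidedness is not stated, so two-sided is assumed. The only sample-size figure is a maximum of 5,400 (12.9). The Table 1 allocations give 200 + 900 + 1,200 + 1,000 + 300 + 250 + 900 = 4,750, which does not reproduce 5,400. The lower total is used below and 5,400 is checked as a variant. No SD, effect size or expected imbalance is given.

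**Assumptions.** The agents are identical. The SD of image quality is 0.6 or 0.7. The share of obese patients differs between groups by Δp, and images of obese patients score d points lower.

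**Formulas.**
- Bias: b = Δp × d.
- Standard error: SE = SD × √(1/n1 + 1/n2).
- Chance of p < 0.05: Φ(b/SE − 1.96) + Φ(−b/SE − 1.96). With b = 0 this is 5.0%, as it should be.

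**Pooled comparison, 2,375 versus 2,375.** SE = 0.6 × √(2/2,375) = 0.0174, or 0.0203 with SD 0.7.

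| Δp × d | b | SD 0.7 | SD 0.6 |
|---|---|---|---|
| 0.05 × 0.2 | 0.010 | 7.8% | 8.9% |
| 0.10 × 0.2 | 0.020 | 16.6% | 21.0% |
| 0.15 × 0.2 | 0.030 | 31.5% | 40.6% |
| 0.15 × 0.3 | 0.045 | 60.1% | 73.4% |
| 0.20 × 0.3 | 0.060 | 84.0% | 93.1% |

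In the last row, b/SE = 0.06/0.0174 = 3.45 with SD 0.6. With SD 0.7, a bias of 1.96 × 0.0203 = 0.04 points is enough for about 50%.

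**Variants, from the first to the last row.**
- 30:70 split, N = 4,750: 7.4% to 77.3% (SD 0.7) and 8.2% to 88.5% (SD 0.6).
- N = 5,400, equal split, SD 0.7: 8.2% to 88.3%.

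**Individual agents, SD 0.7, b from 0.02 to 0.06.**
- 2,375 versus 100: 5.9% to 13.4%.
- 2,375 versus 500: 8.9% to 41.4%.

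With SD 0.6 and b = 0.06, 2,375 versus 101 gives SE = 0.061, b/SE = 0.98 and about 17%.

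**Does adjustment cure it, and for what?** This was simulated with 1,000 runs per scenario, 14 centres at the Table 1 caps, scores rounded to 1-4, linear models, identical agents, SD 0.7 before rounding, obese share 15% versus 30% and a deficit of 0.3. In the second row, centres also differ in rating level (SD 0.2) and in the share of patients given each agent.

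| Scenario | Unadjusted | BMI | BMI + centre |
|---|---|---|---|
| BMI the only confounder | 52% | 4.0% | 4.4% |
| Centres also differ | 52% | 38% | 4.8% |

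BMI alone is therefore not a sufficient covariate.

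**Diagnostic confidence.** No rate was computed. The outcome is a within-patient change, which removes stable patient effects on the level. The possible gain is still capped at 100 minus the unenhanced score, so a different mix of indications can shift the mean change.

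**The case against.** The strongest reply is that section 12.6 is silent on covariates and does not prescribe an unadjusted analysis. It names no test and no model, and nothing in it forbids adjustment. A statistical analysis plan, which was not available for this review, might supply the covariates. That stands: a reader might infer that the protocol mandates a raw comparison, and the text does not say so. What remains is that section 12.6 fixes the contrasts, the alpha and the multiplicity position, lists plain averages and proportions, and defers only Stage 2. Following the text as written can produce a confounded result.

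The second reply is that the protocol disclaims formal hypothesis testing. This limits the status of the result to exploratory, but it does not change how a difference flagged at alpha 0.05 will be read.

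A reader might also infer three further points that the documents do not support:
- **A comparative secondary objective.** Section 5.2 says only that effectiveness and safety are to be assessed. The comparison enters through sections 10.2 and 12.6.
- **Agent choice known to follow BMI.** Section 10.1 provides for recording such a preference; it does not say that one exists. Section 8.2 says that the investigator chooses, not that the choice varies from patient to patient within a centre.
- **Imbalance hidden from view.** Section 12.5.3 tabulates use by BMI, organ and indication, so imbalance will be visible. It will not be corrected.

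**Conclusion.** The concern holds as a gap in section 12.6: a significance-level comparison of agents chosen by investigators, with no named control for confounding, while the relevant variables are collected and used only descriptively.

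The size is conditional. With 4,750 patients split equally and SD 0.6 to 0.7, the chance of a spurious pooled difference in image quality is about 8-9% under mild imbalance and 84-93% under strong imbalance. It would be wrong to quote the upper end as the expected error rate, because the protocol gives no information on the imbalance or the deficit. For an individual agent with about 100 cases the inflation is modest, at most about 17% under the strongest assumption examined. For change in diagnostic confidence the direction of the argument is the same, but the exposure is smaller and has not been quantified.

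**What to change.** In section 12.6, base the between-agent comparison on models using data the study already collects: proportional-odds for image quality and linear for change in diagnostic confidence. Each should contain agent group, centre, MRI versus MRA, organ or system, indication group, BMI and age. The centre is coded in the subject number (8.2), and the examination type is implied by the two-column image-quality scale (10.2). Report adjusted differences with 95% CIs, labelled exploratory. Give the unadjusted figures for description only, without p-values.

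The cost is a paragraph in section 12.6 and a little more analysis work, with no new data. Intervals will widen where centre nearly determines which agent is used, because such centres say little about the difference between agents. Adjustment covers only what is measured; it does not remove the effect of local readers who are not blinded to the agent (8.4).

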The first 25 consecutive patients for which Clariscan is used and the first 25 consecutive patients for which any other GBCAs (all together 25 patients) is used, the images will be transferred for storage to allow a blinded image to read by an expert MR radiology panel to be performed in a future analysis. If the recruitment is less than 25 for either group, then the total images done for the group (Clariscan or GBCAs) during the recruitment period will be transferred. If a patient has repeat imaging for technical reasons and the image is not readable and has been repeated for same indication/reason, then the second readable image will be transferred for storage and analysis.

Investigator: the MR Radiologist; one investigator per centre.

Where a radiology team has multiple physicians involved in the patients' diagnosis and contrast media selections, the site investigators should appoint a single overarching Principal Investigator of the Centre.

Alternatively the study can be focused on a specific patient group under the responsibility of a single physician, as most appropriate to the local circumstances. Cumulative information

collected for the investigator at the end of the study refers to his/her practice during the recruitment period of the study (date of first patient and date of last patient recruitment).

Centre: the institution, hospital or private centre where the study investigator is practicing during the study and patients are recruited for the study from the centre. Cumulative data will be recorded on the eCRF for this centre for the period of recruitment (date of first patient and date of last patient recruitment).

[figure not shown]
Centres with electronic medical record (EMR), picture archiving and communication system (PACS), or any other system in place to collect the cumulative data at the end of the study and compatible for image transfer.

Table 1 Maximum Number of Patients Per Country

Country	Number of Centres	Maximum Number of Patients Allocated to Centres
Norway	1	200
Germany	2	300 + 600 = 900
Spain	3	500 x 2 + 200 = 1200
Italy	3	500 + 400 + 100 = 1000
Portugal	1	300
Poland	1	300 x 3 = 900
France	1	250

An overview of study procedures is presented in [Figure 1](#).

Figure 1 Study Diagram

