10.2 Effectiveness Assessments

Effectiveness will be assessed as Clariscan vs all GBCAs together and Clariscan vs individual GBCA. The assessment will be done in 2 stages:

Stage 1: by the local radiologist and nurse/technician

Stage 2: by a panel of 3 MR experts, blinded to the use of GBCAs independently for the first 50 images transferred to GEHC. The first 25 images of Clariscan and first 25 images all other GBCAs will be used for the analysis as 1:1 ratio. This analysis will be performed at a later date and not part of the initial read out of the study.

Stage 1

Three parameters will be assessed for effectiveness of GBCAs, including Clariscan, by local radiology (A & B) and technician/nurse (C) as first stage of assessment:

- A- Image quality reported by the local radiologist.
- B- Diagnostic confidence reported by the local radiologist.
- C- Customer satisfaction survey reported by the local nurse/radiology technician recorded once per centre during the study for each GBCA used at the study centre, including generics.

A- Image quality reported by the local radiologist

Quality of image will be assessed by the local reporting radiologist on a 4-point Likert scale.

This is based on literature review for the assessment of CE-MR images. The definition for cardiovascular MRA and MRI images are on a 4-point Likert scale and defined in following section.

MRA: [[Hansmann et al. 2014](#)]: For the qualitative assessment, blinded readers assessed image quality on a scale of 1 to 4:

- 1 = poor image quality and blurring of the arterial segment
- 2 = fair image quality, inadequate arterial enhancement for confident diagnosis
- 3 = good image quality and arterial enhancement, adequate for confident diagnosis
- 4 = excellent image quality and arterial enhancement, for highly confident diagnosis

MRI: [[Maravilla et al. 2017](#)] used the following definition for overall visualisation and characterisation of the lesion (or most representative lesion, i.e., enhancing and/or largest if there was >1 lesion present) were assessed on a 4-point scale:

- 0 = poor, inadequate
- 1 = fair, partial
- 2 = good, adequate
- 3 = excellent

Based on the literature review in this study, image quality will be captured on the following 4-point scale:

	MRI	MRA
1	poor, inadequate;	poor image quality and blurring of the arterial segment;
2	fair, partial	fair image quality, inadequate arterial enhancement for confident diagnosis

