3	good, adequate;	good image quality and arterial enhancement, adequate for confident diagnosis;
4	excellent	excellent image quality and arterial enhancement, for highly confident diagnosis)

The results will be reported as comparison of Clariscan to all GBCAs and Clariscan vs individual GBCA if the cohort is bigger than 100 cases.

B- Diagnostic confidence reported by the local radiologist

For each patient based on the **most representative lesion**. All available sequences (e.g., fluid attenuation inversion recovery [FLAIR], T2, and T1 with and without contrast administration) will be available for readers to review and evaluate. **Before reviewing the CE-MR image**, the radiologist will be asked to enter the confidence to make a diagnosis for the patient as a whole number between 0% to 100% based only on the non-enhanced image. The radiologist will then enter the diagnostic confidence as a whole number between 0% to 100% after the CE-MR scan results are read. This will be used to calculate the change in diagnostic confidence in this study by the local radiologist for all GBCAs including Clariscan. The results will be reported as comparison of Clariscan to all GBCAs and Clariscan vs individual GBCA if the cohort is bigger than 100 cases.

C- Customer satisfaction survey reported by the local nurse/radiology technician recorded once per centre during the study for each GBCA used at the study centre, including generics

Reported once per centre by MR nurse/technician from the investigator's staff - Quality of packaging including bottles, syringe, marking, pack size available. This will be recorded once for each GBCA used at the study centre as an overall impression and rated as:

[figure not shown]
1 = can be improved

2 = good

3 = excellent

The results will be reported as comparison of Clariscan to all GBCAs and Clariscan vs individual GBCA.

Figure 3 Effectiveness Assessments

Stage 2 (to be performed at a later date): assessment by a panel of 3 MR experts, blinded to the use of GBCAs independently for the first 50 images transferred to GEHC. The first consecutive 25 images of Clariscan and first consecutive 25 images all other GBCAs will be used for the analysis as 1:1 ratio.

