A subgroup of patients will be selected to transfer the anonymised images to GEHC through AGMednet. The images will be archived at GEHC to be analysed at a later date by an expert MR radiologist panel to assess the quality of images. The first 50 images will be transferred in 1:1 ratio for Clariscan and other GBCAs, i.e., the first consecutive 25 images for Clariscan and the first consecutive 25 images of the other GBCAs (excluding liver-specific GBCAs). In total, a maximum of 850 patients' images will be transferred from all study centres. If sufficient number of images (25) for Clariscan or other GBCA group are not acquired in 3 months, the recruitment will stop at 3 months and all images for either group will be transferred for blinded read.

- Collective anonymised and blinded images for all GBCAs including Clariscan from all centres will be assessed and analysed by a panel of 3 MR expert radiologists. There will be no centre-level analysis or comparison for Clariscan and other GBCAs.
- Quality of images reported by 3 MR expert radiologists blinded to the GBCAs use and inter-observer variability.
- Correlation between local radiologist rating and blinded radiologist rating.

This analysis will not be part of the initial read out of the study and will be performed at a later date.

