12 STATISTICAL METHODS AND PLANNED ANALYSIS

The data will be analysed by the CRO. Any data analysis carried out independently by the investigator should be submitted to the sponsor before publication or presentation.

Data from participating centres in this protocol will be combined so that an adequate number of subjects will be available for analysis. The data will be summarised with respect to demographic and baseline characteristics, efficacy observations and measurements, safety observations and measurements.

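### Sections 10.2 and 12.6 define the same Clariscan comparison differently, and an unadjusted pooled comparison could confound agent with centre

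*Protocol*

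**What the plan says.** Two sections of the protocol describe the Stage 1 effectiveness comparison.

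- **Section 10.2** opens with "Effectiveness will be assessed as Clariscan vs all GBCAs together and Clariscan vs individual GBCA". For image quality, and again for diagnostic confidence, it says results will be reported as "comparison of Clariscan to all GBCAs and Clariscan vs individual GBCA if the cohort is bigger than 100 cases".
- **Section 12.6** summarises the data for all agents pooled, and separately "for non-Clariscan GBCAs pooled, and for all individual GBCAs administered during the study, including Clariscan". It then fixes the comparisons: "Clariscan vs non-Clariscan GBCAs pooled and Clariscan vs each individual GBCA) will be assessed at an alpha of 0.05". The next sentence reads "However, no formal statistical hypotheses will be tested and no adjustments will be made for multiplicity". The synopsis repeats this text.

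On the setting of these comparisons:

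- Section 8.2 leaves the choice of agent to the site.
- Section 8.4 plans no blinding.
- Section 10.2 has the local reporting radiologist score image quality on a 4-point scale and confidence from 0% to 100%.
- Section 6.1 states "Investigator: the MR Radiologist; one investigator per centre", but lets a team of several physicians work under one Principal Investigator, or lets the study focus on a specific patient group at a centre.
- Section 12 states "Data from participating centres in this protocol will be combined so that an adequate number of subjects will be available for analysis".

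**The concern.** One planned comparison has two definitions. They differ in the comparator (a pool with or without Clariscan) and in which individual agents are compared (those above 100 cases, or every one). An analyst could follow either section and claim to have followed the protocol. Section 12.6 also sets a significance level while saying nothing is formally tested, so it is unclear what a result below 0.05 is allowed to mean.

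The second issue is centre. Agent, rater, scanner and case mix all come from the centre. If centres that use more Clariscan also tend to score higher, or see easier cases, combining centres without adjustment shows a Clariscan difference that is really a difference between centres. This is a sponsor's study of its own product beside competitors, so a nominally significant result is likely to be noticed.

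**Working it through.** The 0.05 level is a choice, and the protocol gives no power, effect size or standard deviation. There is therefore no calculated figure to reproduce.

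**1. The two definitions side by side**

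| Element | Section 10.2 | Section 12.6 |
|---|---|---|
| Pooled comparator | all GBCAs | non-Clariscan agents only |
| Individual agents (image quality, confidence) | only cohorts above 100 cases | every agent |
| Significance level | none given | 0.05, with no formal hypotheses |

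Section 12.6 lists the all-agent pool and the non-Clariscan pool as different groups, so the two terms are not synonyms there. If k other agents are used and m of them exceed 100 cases, each outcome has 1 + k comparisons under 12.6 and 1 + m under 10.2, with m ≤ k and no multiplicity adjustment.

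**2. Effect of the comparator, reading 10.2 literally**

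Let s be the Clariscan share of patients, and C and N the mean scores with Clariscan and with the other agents.

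Mean over all GBCAs = sC + (1 − s)N, so C − mean over all = (1 − s)(C − N).

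The part of the difference that remains is 90% at s = 0.1, 70% at 0.3, 50% at 0.5, 30% at 0.7 and 10% at 0.9. Under the 12.6 comparator it is 100%.

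**3. Effect of centre if no adjustment is made**

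Input from the protocol: the 14 centre caps in the synopsis version of Table 1 (200; 300, 600; 500, 500, 200; 500, 400, 100; 300; 250; 300, 300, 300), which sum to 4,750.

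Assumptions not in the protocol:
- every centre fills its cap;
- scores are continuous with total variance 1, and centre variance equals the intra-centre correlation (ICC);
- there is no true agent effect;
- the mean Clariscan share is 50%, either the same everywhere or drawn by centre from Beta(10,10), Beta(2,2) or Beta(0.5,0.5).

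The SD of the share is √(0.25/(a + b + 1)): √(0.25/21) = 0.11, √(0.25/5) = 0.22 and √(0.25/2) = 0.35.

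There were 2,000 simulated studies per setting, and tests were two-sided at 1.96. False-positive rate of the unadjusted two-sample test:

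| ICC | same share | SD 0.11 | SD 0.22 | SD 0.35 |
|---|---|---|---|---|
| 0 | 0.048 | 0.059 | 0.046 | 0.051 |
| 0.01 | 0.048 | 0.073 | 0.133 | 0.245 |
| 0.05 | 0.050 | 0.144 | 0.340 | 0.524 |
| 0.10 | 0.058 | 0.227 | 0.482 | 0.647 |
| 0.20 | 0.052 | 0.314 | 0.619 | 0.756 |

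With centre as a fixed effect, the rate lies between 0.041 and 0.058 in all 20 settings. The simulation standard error at 0.05 is √(0.05 × 0.95/2000) = 0.005, so these rates are compatible with 0.05.

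The spurious differences are small in absolute terms. At ICC 0.05 the mean absolute difference is 0.031, 0.049 and 0.074 SD for the three varying-share columns, against 0.024 SD with equal shares. With several thousand patients, differences of that size are often significant.

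**The case against.** Four points weigh on the other side.

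- **The centre charge rests partly on silence.** A reader might infer that the p-values will reflect centre differences. The protocol does not support that. It names no test or model and excludes no adjustment. Combining data is ordinary multicentre wording, and model terms are commonly left to the statistical analysis plan, which was not available for this review. Inflation needs an unadjusted test, scores that differ by centre and a Clariscan share that differs by centre; the first row and first column of the table show about 5% when either kind of variation is absent. This objection stands, so the centre issue is a risk to close, not an error made.
- **Dilution does not reach the comparison made at 0.05.** A reader might infer that the section 12.6 result is diluted. It is not, because its pool excludes Clariscan. Section 10.2 sets no test, and its wording may be loose shorthand for the other agents: sections 6.1 and 9.2 call the two image groups Clariscan and GBCAs. But within the diagnostic confidence text, 10.2 itself uses all GBCAs as a term that includes Clariscan, and 12.6 keeps the pools apart. The wording conflict stands.
- **Stage 2 is separate.** "There will be no centre-level analysis or comparison for Clariscan and other GBCAs" might be read as ruling out centre adjustment. It concerns the later blinded read, which has its own analysis plan, and most naturally bars per-centre reporting. It is no evidence about the Stage 1 comparison.
- **One investigator is not one rater.** Section 6.1 allows several physicians per centre, so scores within a centre need not come from one reader. Scanner and case mix would still be shared.

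Effectiveness is also a secondary objective, and section 12.9 says that the sample size has no statistical basis. Comparing at 0.05 without multiplicity adjustment is openly disclosed. That limits the severity but does not reconcile the sections.

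**Conclusion.** The concern holds in two parts of different strength.

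**Firm:** sections 10.2 and 12.6 disagree on the comparator and on which individual agents are compared, and the significance level in 12.6 sits awkwardly beside its statement on hypotheses. These follow from the text alone. Read literally, the 10.2 comparator keeps only (1 − s) of the difference, half at a 50% share.

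**Conditional:** site-chosen agents, unblinded local scoring and combined centres create a real opportunity for centre confounding. If the comparison is unadjusted and both scores and Clariscan share vary by centre, the false-positive rate is about 7–25% at ICC 0.01 and 14–52% at ICC 0.05. These rates rest on assumed ICCs and share distributions and on full enrolment to the caps. With centre adjustment the rate is about 5%.

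The sponsor should correct this before analysis. It does not affect the primary, descriptive objective.

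**What to change.** 1. In section 10.2, make the pooled non-Clariscan agents the comparator, as in 12.6. Make the same change where section 10.3 sets Clariscan against GBCAs; section 12.7 already separates the two pools.
2. Apply the rule of more than 100 cases to individual-agent comparisons of image quality and diagnostic confidence in both 10.2 and 12.6.
3. State in 12.6 that every Clariscan contrast is estimated within centre, with centre as stratum or fixed effect, reported with a 95% confidence interval and labelled descriptive.

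The cost is a change of wording and model-based tables. No new data are needed, because the subject number in section 8.2 already identifies the centre. The drawback is that a centre using only one agent contributes nothing to the within-centre contrast, so the number of such centres should be reported beside the estimate.

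### Diagnostic confidence is compared between non-randomised GBCA groups as a raw change on a scale capped at 100%, so unequal non-enhanced confidence can push the alpha 0.05 comparison well above 5% with identical agents

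*Protocol*

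**What the plan says.** Section 10.2, part B, collects two ratings per patient. Before the contrast-enhanced image is reviewed, "the radiologist will be asked to enter the confidence to make a diagnosis for the patient as a whole number between 0% to 100"%, using the non-enhanced image only. Then: "The radiologist will then enter the diagnostic confidence as a whole number between 0% to 100% after the CE-MR scan results are read". The section says that the two are used to calculate a change, and that results are reported as a comparison of Clariscan with all GBCAs, and with an individual GBCA if its cohort exceeds 100 cases.

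Section 12.6 lists among its summaries "The average change in diagnostic confidence (diagnostic confidence using CE-MR enhanced image minus diagnostic confidence using the non-enhanced image"). It also plans to judge "Statistical differences in image quality and diagnostic confidence between groups" against a 0.05 significance level. Two kinds of contrast are named: "Clariscan vs non-Clariscan GBCAs pooled and Clariscan vs each individual GBCA". The section adds that "no formal statistical hypotheses will be tested and no adjustments will be made for multiplicity". The synopsis repeats this.

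The groups are not randomised. Under section 8.2, "the choice of GBCA will be made by the investigator at the site as part of clinical practice".

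The protocol names no test, model or covariate for this comparison. It neither plans nor excludes adjustment for non-enhanced confidence.

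**The concern.** The largest change a patient can show is 100 minus the non-enhanced score. A patient rated 90% without contrast can gain at most 10 points; one rated 40% can gain 60. The non-enhanced rating involves no GBCA, yet it limits the outcome by which the agents are compared.

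Because the agent follows clinical choice, one agent may be used more often where the diagnosis is already clear. Section 10.1 itself records the reason for using a GBCA and preference for an agent due to BMI, and section 7.2.2 lets a centre restrict the study to a specific patient group. Equal non-enhanced confidence across agents therefore cannot be assumed. An agent used in clearer cases would tend to show a smaller mean gain, and one used in harder cases a larger gain, with no difference in performance. At stake is a significance statement, in either direction, about the sponsor's product on a secondary objective.

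**Working it through.** **No design figure to reproduce.** The protocol gives no effect size, SD or power for this comparison, and section 12.9 says that the sample size has no statistical basis.

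**Inputs from the protocol.** Alpha is 0.05 (two-sided assumed; sidedness is not stated). The scale is whole numbers from 0 to 100. Individual comparisons need more than 100 cases. The Table 1 caps sum to 200 + 900 + 1,200 + 1,000 + 300 + 250 + 900 = 4,750, so an even split is 2,375 per group. The text allows up to 5,400, or 2,700 per group.

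**Assumed, because the protocol is silent.** Slope b of enhanced on non-enhanced confidence, SD of the change, and baseline difference D in points.

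**Step 1: analytic.** If identical agents share enhanced = a + b × non-enhanced, the expected difference in mean change is, in absolute size, (1 − b) × D. With SE = SD × √(1/n1 + 1/n2) and z = (1 − b)D/SE, the rejection rate is Φ(z − 1.96) + Φ(−z − 1.96).

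Worked case: b = 0.5, D = 2, SD = 20, 2,375 per group. The shift is 0.5 × 2 = 1.0 point; SE = 20 × √(2/2,375) = 0.580; z = 1.72; rejection rate 0.406.

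| n1 / n2 | SD | b | D | Rejection rate |
|---|---|---|---|---|
| any | any | 1 | any | 0.05 |
| 2,375 / 2,375 | 15 | 0.5 | 2 | 0.632 |
| 2,375 / 2,375 | 20 | 0.5 | 2 | 0.406 |
| 2,375 / 2,375 | 25 | 0.5 | 2 | 0.281 |
| 2,375 / 2,375 | 20 | 0.8 | 2 | 0.106 |
| 2,375 / 2,375 | 20 | 0.2 | 2 | 0.787 |
| 2,700 / 2,700 | 20 | 0.5 | 2 | 0.451 |
| 100 / 100 | 20 | 0.5 | 2 | 0.064 |
| 100 / 100 | 20 | 0.2 | 2 | 0.087 |
| 1,000 / 100 | 20 | 0.2 | 2 | 0.119 |
| 100 / 100 | 20 | 0.5 | 5 | 0.143 |
| 1,000 / 100 | 20 | 0.5 | 5 | 0.222 |

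**Step 2: simulation on the bounded scale, identical agents.** Non-enhanced mean 60, SD 20; contrast closes half the gap to 100; residual SD 10; scores rounded and limited to 0–100. A Welch test on the change is compared with regression of enhanced confidence on group, non-enhanced score and its square, with robust SEs. Ranges are over repeated sets of runs.

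- 2,375 per group, D = 1, 2, 5: raw change rejects in 23–25%, 71–73% and 100%. The spurious differences are 0.5, 1.0 and 2.6 points. Adjusted: 3–6%.
- Contrast closes 30% or 80% of the gap, D = 2: raw 47–50% and 87–89%.
- 1,000 vs 3,750, D = 1, 2, 5: raw 18%, 55–56% and 100%.
- 101 vs 101, D = 5: raw 26–28%; adjusted 3–4%.
- Ceiling only (+20 points for everyone, cut off at 100), 2,375 per group, D = 2 and 5: raw 22–23% and 89–92%; adjusted about 5%.

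The implied SD of change in the first scenario is √((0.5 × 20)² + 10²) = 14.1, which is low. Step 1 shows how the rate falls as the SD rises.

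**Step 3: noisy baseline rating.** The adjusted rates in step 2 are nominal because enhanced confidence was generated from the recorded baseline score. If the outcome instead depends on an underlying score recorded with reliability 0.8 (assumed), with D = 5 and 2,375 per group:

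- half of the gap closed: raw 100%, adjusted 36–41%;
- additive gain with a cap: adjusted 67–70%, raw from 8–9% up to about 60% depending on how close patients start to the ceiling.

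**The case against.** The strongest objection is that the protocol fixes a summary measure, not an unadjusted test. No model is named, an SAP that is not shown may specify one, and regressing the change on group plus non-enhanced score gives the same group coefficient as regressing enhanced confidence on both. This stands: a reader might infer that the plan commits to an unadjusted comparison, and the documents do not establish that. But sections 10.2 and 12.6 do name the raw change as the compared quantity and attach alpha 0.05, and section 12.6 refers only Stage 2 to a separate analysis plan. The protocol text should not leave the unadjusted reading open.

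Second, a reader might infer that the test rejects whenever baselines differ. It does not. With slope 1 and no ceiling the rate is 5% for any imbalance, and with individual cohorts near 100 a 2-point imbalance gives about 5–12% at SD 20. The larger rates need assumed inputs and large groups, and the artefact behind them may be about 1 point on a 100-point scale.

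Third, in non-randomised groups neither change scores nor baseline adjustment is right under all conditions. This also stands: with a noisy baseline and additive gain, adjustment can do worse than the raw change. That is why both analyses should be shown.

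Fourth, the protocol disclaims formal hypotheses and the objective is secondary. This limits the weight of the point, but an alpha of 0.05 still invites readers to take a difference as significant.

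**Conclusion.** The point holds in a limited form. Comparing raw change on a capped scale between groups formed by clinical choice can reject well above 5% with identical agents. Under the step 2 assumptions, a 2-point imbalance at 2,375 per group gives roughly 20% (ceiling only) to 90% (80% of the gap closed). A shallower departure from slope 1 gives less: 0.106 at b = 0.8 and SD 20. Imbalance, slope and SD are all assumptions, and the even split of every capped patient is the largest case Table 1 allows.

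It would also go too far to conclude that baseline adjustment makes the comparison valid at 5%. It addresses the baseline and ceiling mechanism only, and imperfectly if the non-enhanced rating is noisy. Confounding by indication, organ or centre, and the unblinded local rating, remain. The change is worth making because it is cheap and the covariate is already planned for collection in every patient.

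**What to change.** In section 12.6 and the synopsis:

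- Keep the mean change as a descriptive summary, with mean non-enhanced confidence by GBCA beside it.
- Base the between-GBCA comparison on a model adjusted for the same patient's non-enhanced confidence (linear plus a quadratic or spline term, robust SEs), reported as a difference with its 95% CI.
- Report the unadjusted change comparison alongside as a sensitivity analysis.
- State that the adjustment removes only the baseline and ceiling mechanism, is imperfect if the non-enhanced rating is noisy, and does not address confounding by indication, organ or centre or the unblinded local rating, so the result is exploratory.

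The cost is a few sentences of text and one added covariate, with no new data, patients or procedures. The adjusted difference is slightly less direct to read than a raw change, which stays in the tables.
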